## 2 INTRODUCTION

### 2.1 STUDY RATIONALE

Little is known about the relationship between dietary sodium and gut microbiome ecosystem in humans; or how it might be altered by incremental changes in sodium intake. The GENE-FORECAST-SIT study will be the first to test the hypothesis that changes in dietary sodium intake are sufficient to influence the composition of the gut microbiome in association with sodium-induced changes in vascular function, epigenome, transcriptome and blood pressure in African Americans.

### 2.2 BACKGROUND

There is an abundant body of evidence from longitudinal population studies that have established a striking relationship between certain dietary patterns and the risk of cardiovascular disease. Diets rich in fruits, vegetables, whole grains, fish, nuts and fats such as olive oil have been associated with reduced risk of cardiovascular disease and adverse outcomes. Similarly, controlled dietary intervention trials with the DASH diet have demonstrated that a low-sodium diet that is rich in fruits, vegetables, whole grains and low-fat dairy products is an effective approach to reducing blood pressure in hypertension patients. It is noteworthy that African Americans appeared to have the greatest benefit from this dietary intervention. However, the molecular mechanisms that mediate the effect of diet on blood pressure and the development of cardiovascular disease remain to be further elucidated.

It is well established that increased dietary sodium can predispose to an increase in blood pressure; particularly in ‘salt-sensitive’ individuals. In most individuals there are a powerful series of homeostatic systems (renal, neurohumoral, vascular) that function to maintain the normal set-point blood pressure across a very broad range of dietary sodium intakes. Yet, a subset of ‘salt-sensitive’ individuals exhibit changes in vascular function and modest elevations in blood pressure in response to relatively modest changes in dietary sodium intake. It is noteworthy that several studies have suggested an apparent increased prevalence of ‘salt-sensitive’ blood pressure among African Americans.

Commonly used animal models of hypertension often employ high dietary sodium intake as a means of inducing sustained hypertension. The Dahl Salt-Sensitive Rat is a genetic model of hypertension that becomes hypertensive upon the administration of a high-sodium diet; whereas the genetically related Dahl Salt-Resistant Rat remains normotensive despite the high dietary sodium intake. Although there are multiple factors that appear to mediate this genetic predisposition to salt-sensitive hypertension, an intriguing recent report has noted a striking difference between the gut microbiome in Dahl salt-sensitive vs salt-resistant animals. In addition, recent studies have demonstrated a relationship between increased dietary sodium intake and modulation of the immune system in animal models. The proposed project seeks to further extend the working hypothesis that the effect of dietary sodium on vascular function and blood pressure may be modulated by the gut microbiome and its influence on the immune system. The selected dosage of sodium chloride is based on prior research.

It is becoming increasingly clear that human biology and pathobiology is influenced in part by the trillions of microbes that co-exist within our bodies in a mutually beneficial manner. The microbe ecosystems that live within the human gastrointestinal tract are shaped by our dietary intake that supports the predominance of certain flora relative to others. Conversely, the microbe composition of each individual’s gut can influence the digestion and generation of certain metabolites from certain foods. The various patterns of gut microbiome composition have been implicated in the regulation of the immune system as well as the pathogenesis of obesity, autoimmune disorders and cardiovascular disease. For example, Stan Hazen’s team has shown striking differences in the human microbiome between vegetarians and those who are frequent ‘meat-eaters’. This dietary difference is associated with differential generation of a microbe metabolite, trimethylamine-oxidase (TMAO). Increased generation of the microbe metabolite, TMAO, is associated with increased risk of cardiovascular disease. Moreover, it has been shown that pharmacologic inhibition of the generation of this gut microbe metabolite attenuates atherogenesis in animal models. Taken together, these clinical and animal model studies suggest a causal link between dietary patterns, the gut microbiome and cardiovascular disease.

## 2.3 RISK/BENEFIT ASSESSMENT

### 2.3.1 Known Potential Risks

Risk of participating in the study is minimal given the benefit to the scientific community derived from findings related to the effect of salt on vascular, blood pressure and microbiome among African Americans. The salt capsules are generally safe and well tolerated but side effects can occur -including discomfort while swallowing, increased thirst, indigestion, nausea, vomiting, headaches, mild elevations in blood pressure, mild changes in blood chemicals (electrolytes), lightheadedness, tiredness, mild swelling of arms/legs, and/or diarrhea. Although it would be very rare to have an allergic reaction to the capsules, any time a new medication is

introduced there is a small chance of an allergic reaction which would most commonly manifest itself as a rash.

See Section 2.3.3 for detailed description of risks

### **2.3.2 Known Potential Benefits**

**There is no direct benefit to the participant for participating in the study. However, findings generated from the study will add to the scientific body of knowledge regarding the effect of salt among African Americans who have a disproportionately higher prevalence of cardiovascular disease**

### **2.3.3 Assessment of Potential Risks and Benefits**

The risks are very minor and include:

Vascular function testing and 24-hour blood pressure monitor: Subject may experience brief discomfort, pain or tingling sensations when the blood pressure cuff is inflated to reduce blood flow to the hand for a few minutes during the vascular function tests and/or 24-hour blood pressure monitor.

Phlebotomy: Transient discomfort and minor bruising may occur when blood is drawn.

Microbiome collection:: Collection will comprise of skin, saliva and stool samples utilizing Norgen kits. These tests carry very minor risks, with the transient mild skin irritation at the sites where your skin is swabbed although this is very unlikely.

Salt capsules: Sodium chloride is approved by the Food and Drug Administration (FDA) for a variety of clinical uses and is available over the counter (OTC). The capsules given as part of this study contain sodium chloride (salt) in powder form or placebo. The amount of salt added to subject's usual daily diet as part of this study is equivalent to about half a teaspoon of salt or a packet of Ramen chicken noodle soup. The salt capsules are generally safe and well tolerated but side effects can occur including discomfort while swallowing, increased thirst, indigestion, nausea, vomiting, headaches, mild elevations in blood pressure, mild changes in blood chemicals (electrolytes), lightheadedness, tiredness, mild swelling of arms/legs, and/or diarrhea. Although it would be very rare to have an allergic reaction to the capsules in this study, any time a new medication is taken there is a small chance (less than 1 person out of 1000 treated) that you could have an allergic reaction which would most commonly manifest itself as a rash.

The GENE-FORECAST-SIT staff will monitor subjects during study participation to detect any potential serious adverse reactions to the salt capsules.

24 Hour food intake recall: Subjects may be asked a series of questions by staff from the Clinical Center Nutrition Department to recall any foods or beverages they may have eaten or drank over the past 24 hours. There may be a minor psychological discomfort of not being able to recall any food or beverage item questions over the past 24 hours.

**Mouth:** At each clinical center visit, saliva samples from subjects mouth will be collected by passive drool or spit using a sterile collection tube. Providing study samples of these specimens that the body normally excretes will not cause any additional pain or discomfort.

**Stool:** Subjects will be provided with a stool specimen collection kit prior to their visit. There may be some physical discomfort of inability to obtain sample (e.g., constipation). Providing study samples of these specimens that the body normally excretes will not cause any additional pain or discomfort.

**Urine:** Subjects will be asked to give a urine sample in a sterile cup provided at the NIH Clinical Center to test for urine chemistries (e.g., potassium, chloride, sodium). There may be physical limitations in inability to provide sample (e.g. dehydration). Providing study samples of these specimens that the body normally excretes will not cause any additional pain or discomfort.

**Psychophysical Taste Task with sucrose and salt detection thresholds and preference:** Sucrose and salt detection thresholds and preference will be assessed to get subject responses to sweetness or saltiness. There may be a discomfort of tasting solutions and repeated spitting action to discard in waste receptacle.

**Physical activity and sleep questionnaire:** Subjects will be asked a series of questions related to their physical activity and sleep. They may experience minor psychological discomfort of answering personal questions regarding their physical activity and sleeping habits.

GENE-FORECAST-SIT staff will closely monitor the study participant in order to detect any potential severe adverse reactions to study medication. Specifically, GENE-FORECAST-SIT staff will contact individual study participant +/-2 days a week to anticipate missed calls and occasional inability to reach participant during the treatment phase of the trial to inquire about any severe adverse reactions. Participant will also be given the direct mobile telephone number of GENE-FORECAST-SIT staff to discuss any adverse reactions.

The risk of minimal potential risks outweighs the benefit of scientific knowledge gained from the effects of sodium on cardiovascular health, taste genotype and microbiome in African Americans.

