It is estimated that participants will spend approximately 5 hours at the Clinical Center during baseline and approximately 3 hours during each of the subsequent visit. Obtaining and explaining the informed consent will take about 20-30 minutes. Female prospective participant who signs consent and subsequently test positive for pregnancy prior to randomization will not be enrolled in the study. Administering the baseline questionnaires will take about 1.45 hours and 75 minutes for the 24-hour diet recall and taste assessments for each subsequent visit. The clinic visit

assessment, plus vascular function test and microbiome collection, will take about 1.30 hours. A member of the clinical study staff will follow-up with participant one week after visit to assess any adverse reaction to consuming intervention product. All procedures and details for each can be found in the study's Manual of Operation (MOP).

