#### 8.2.8 Time Period and Frequency for Event Assessment and Follow-Up

The occurrence of an AE or SAE may come to the attention of clinical study staff during study visits and follow-up after study visit to assess reaction(s) to intervention product.

All AEs including local and systemic reactions not meeting the criteria for SAEs will be captured on the appropriate Case Report Form (CRF). Information to be collected includes events description, time of onset, Staff Clinician's assessment of severity, relationship to study product and time of resolution/stabilization of the event. All AEs occurring while on study will be documented appropriately regardless of relationship. All AEs will be followed to adequate resolution.

Any medical condition that is present at the time that the participant is screened will be considered as baseline and not reported as an AE. However, if the study participant's condition deteriorates at any time during the study, it will be recorded as an AE.

Changes in the severity of an AE will be documented to allow an assessment of the duration of the event at each level of severity to be performed. AEs characterized as intermittent require documentation of onset and duration of each episode.

The study's Physician Assistant will record all reportable events with start dates occurring any time after informed consent is obtained until 7 days (for non-serious AEs) or 30 days (for SAEs) after the last day of study participation. At each study visit, the PI will inquire about the occurrence of AE/SAEs since the last visit. Events will be followed for outcome information until resolution or stabilization.

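### Treatment-phase safety calls cover only severe reactions on an unclear schedule, and no scheduled contact covers most of the 30-day window for serious adverse events

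*Combined protocol and SAP*

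**What the plan says.** **Between visits.** Section 2.3.3 (Assessment of Potential Risks and Benefits) says staff will "monitor subjects during study participation to detect any potential serious adverse reactions to the salt capsules". Later in the same section, staff "will contact individual study participant +/-2 days a week to anticipate missed calls", and the calls are made "during the treatment phase of the trial to inquire about any severe adverse reactions". Participants also receive a way to report for themselves: "Participant will also be given the direct mobile telephone number of GENE-FORECAST-SIT staff to discuss any adverse reactions". Section 8.2 (Efficacy Assessments) describes a further contact: "A member of the clinical study staff will follow-up with participant one week after visit to assess any adverse reaction to consuming intervention product". Table 2 in Section 1.3 lists no telephone contact.

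**At visits.** Section 8.2.8 (Time Period and Frequency for Event Assessment and Follow-Up) has the principal investigator ask at each visit about AEs and SAEs that have occurred since the previous one.

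**What must be recorded.** The same section states: "All AEs occurring while on study will be documented appropriately regardless of relationship". Recording continues for 7 days for non-serious events and "30 days (for SAEs) after the last day of study participation". The section on SAE reporting requires SAEs to be reported whether or not they are thought to be related. Section 8.2.7.1 (Severity of Event) cautions that severe and serious are not the same thing.

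**The concern.** The treatment-phase calls ask a narrower question than the recording duty they serve. Sections 2.3.1 and 2.3.3 list expected capsule reactions that are mostly mild, such as thirst, indigestion and slight limb swelling. A call confined to severe reactions does not prompt for them. Section 2.3.3 also uses serious in one place and severe in another, although the protocol itself separates the two terms.

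The call frequency cannot be carried out as written, so staff could reasonably follow different schedules. At the end of the study, the SAE window outlasts every scheduled contact.

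What is at stake is how complete and how even the side-effect record is. The Independent Safety Monitor reviews safety data by arm (Section 10.5), and that review is only as good as the way events are elicited.

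**Working it through.** **Inputs.** Treatment 2 weeks, washout 3 weeks, treatment 2 weeks (Section 4.1). Four visits, at baseline and at the end of each phase (Table 2). Follow-up one week after a visit (Section 8.2). Recording windows of 7 and 30 days after the last day of participation (Section 8.2.8).

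**Timeline.** 2 + 3 + 2 = 7 weeks, which reproduces the stated length of participation. Visits fall at about days 0, 14, 14 + 21 = 35, and 35 + 14 = 49. If the follow-up applies after every visit, adding 7 days gives contacts at days 7, 21, 42 and 56.

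**Scope of each contact.**

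| Contact | Days | Asks about |
|---|---|---|
| Calls, Section 2.3.3 | treatment phases | severe reactions |
| Follow-up, Section 8.2 | 7, 21, 42, 56 | any reaction to the product |
| Visits, Section 8.2.8 | 14, 35, 49 | all AEs and SAEs |
| Recording duty, Section 8.2.8 | whole study | all AEs, related or not |

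During treatment, a mild product reaction is asked about within about 7 days (follow-up at day 7 or 42, then the visit at day 14 or 49). An event not regarded as a product reaction waits for the visit: up to 14 days in a treatment period, or 35 − 14 = 21 days in washout.

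**Call frequency.** Read as twice a week, the Section 2.3.3 wording gives 2 × 2 = 4 calls per two-week period. Read as weekly with a two-day allowance, it gives 1 × 2 = 2. On the weekly reading the day-7 call coincides with the Section 8.2 follow-up; on the twice-weekly reading the two differ.

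**End of study.**

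| Reading | Last contact | Non-serious window ends; days after last contact | SAE window ends; days after last contact |
|---|---|---|---|
| Participation ends at Visit 4; follow-up made | 56 | 49 + 7 = 56; 0 | 49 + 30 = 79; 23 |
| Participation ends at Visit 4; no follow-up after it | 49 | 56; 7 | 79; 30 |
| Participation ends at the follow-up itself | 56 | 56 + 7 = 63; 7 | 56 + 30 = 86; 30 |

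Even on the first reading, the day-56 contact asks only about product reactions. No scheduled contact after Visit 4 asks about events of other causes, which Section 8.2.8 also requires to be recorded. The safety visit in Section 7.2 does not close the gap: it concerns participants removed early and falls only about a week after the last dose.

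**The case against.** A reader might infer that events the protocol must record are never asked about. The documents do not support this for the on-study period. Every visit after baseline asks about all AEs and SAEs since the previous one, the follow-up covers any product reaction, and participants hold a staff number for any reaction. Two of the listed reactions, blood pressure and electrolyte changes, are also measured at visits.

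A reader might also infer that two conflicting call frequencies are stated. That is not established. Section 2.3.3 contains one ambiguous expression, and its reference to missed calls fits a weekly call with an allowance. The Section 8.2 follow-up is tied to visits and may be a separate contact.

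Further points carry weight. The 30-day limit defines which events are recorded and does not promise active questioning throughout. Staff are blinded and each participant takes both treatments, so no route to differential ascertainment between salt and placebo is shown. Section 9.4.4 plans no safety analysis. Sections 8.2 and 8.2.8.1 leave procedural detail to a manual of operations that is not available here and may settle some of this.

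These arguments limit the size of the point but do not remove it. The call scope remains narrower than the recording duty, the schedule remains unclear in the protocol text, and days 8 to 30 after Visit 4 remain without a scheduled contact.

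**Conclusion.** The point holds as a minor correction to safety-data collection. During the study the consequence is later recall and uneven prompting of mild events. After Visit 4, about 23 of the 30 days in the SAE window rely on spontaneous report, or all 30 on either of the stricter readings.

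The 23-day figure assumes that the last day of participation is Visit 4 and that the one-week follow-up is made after it. The documents give no rate for mild reactions, so the number of events affected cannot be estimated. No primary or secondary endpoint depends on these contacts.

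**What to change.** Reconcile Section 2.3.3 (both statements), Section 8.2 and Section 8.2.8 as follows:

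1. Have the calls already planned ask about any adverse event, in line with the recording duty, and use serious and severe as Section 8.2.7.1 distinguishes them.
2. State one unambiguous contact schedule, say whether the Section 8.2 follow-up is one of these calls or a separate contact, and say whether it applies after Visit 4.
3. Either schedule a closing contact that matches the SAE window or restate the window. The choice is the sponsor's.

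The cost is protocol and call-script wording and at most one extra telephone call per participant. The addendum on transfer of GENE-FORECAST data (Section 12) reports 28 participants enrolled. If enrolment has in effect ended, the study report should instead describe how adverse events were actually elicited, including after Visit 4.

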### 3 OBJECTIVES AND ENDPOINTS

OBJECTIVES	ENDPOINTS	JUSTIFICATION FOR ENDPOINTS
Primary		
What effect does increase dietary sodium intake have on vascular function and microbiome?	Vascular function Microbiome	A sub-set of 'salt-sensitive' individuals exhibit changes in vascular function and modest elevations in blood pressure in response to relatively modest changes in

		dietary sodium intake. Studies have suggested an apparent increased prevalence of 'salt-sensitive' blood pressure among African Americans. The various patterns of gut microbiome composition have been implicated in the regulation of the immune system as well as the pathogenesis of obesity, autoimmune disorders and cardiovascular disease.
Secondary		
What effect does increase dietary sodium have on blood pressure?	Blood pressure	It is well established that increased dietary sodium can predispose to an increase in blood pressure.
What effect does increase dietary sodium have on whole blood epigenome?	DNA methylation RNAseq	DNA methylation is a well-established measure of the epigenome.
What effect does increase dietary sodium have on whole blood and urine transcriptome	RNAseq	RNAseq is a well-established measure of genetic transcriptome.

## 4 STUDY DESIGN

### 4.1 OVERALL DESIGN

This study involves a call-back and recruitment of 40 normotensive participants from the GENE-FORECAST protocol. Those in the upper tertile of vascular stiffness (as assessed by pulse wave velocity measures) will be oversampled. Participants will be randomized to a placebo or salt treatment arm for two weeks (Period 1), followed by a wash-out period for three-weeks, ending with a cross-over to the alternative treatment arm for two weeks (Period 2). The total length of participation is 7 weeks (Figure 1).

#### Study Site:

All study activities will take place at the NIH Clinical Center. The NIH Clinical Center Pharmacy will dispense the treatment and placebo capsules.

#### Statement of hypotheses:

\* Based on population history, it is postulated that the genomic architecture of individuals of African ancestry has been shaped by environmental pressures and natural selection in the context of high ambient temperatures in salt-poor conditions that may predispose to an increased sensitivity and avidity for sodium retention in African Americans.

- \* Increased dietary sodium intake is associated with vascular dysfunction and increased blood pressure in certain sub-sets of normotensive African Americans; and this effect is augmented in individuals with baseline evidence of vascular dysfunction.
- \* Increased dietary sodium intake is associated with changes in the whole blood epigenome as assessed by DNA methylation.
- \* Increased dietary sodium intake is associated with changes in the whole blood and urine transcriptome as assessed by RNA-seq.
- \* Increased dietary sodium intake is associated with changes in the skin, oral and gut microbiome.
- \* Increased dietary sodium intake is associated with whole blood epigenome/transcriptome molecular signature that predisposes to a chronic “pro-inflammatory state.”

